# 2.2 Secondary objective

To investigate if the medication management centre is able to identify patients at risk for a drug-drug-gene interaction. Moreover, it will be investigated whether integrating the MMC into healthcare will lower the adverse drug event rate compared with matched historical control.

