Effectiveness in the prevention of ADRs and the ability to identify drug-drug-gene interactions will be explored as a secondary endpoint by comparing results of the pilot study with those obtained from matched historical controls obtained from the control arm of the U-PGx project. This control arm is suitable as historical control group for the EmPaSafe study because of its alignment in key aspects, allowing for meaningful comparisons:

- Genotyped but not empowered with PGx Data: Participants in the U-PGx control arm were genotyped retrospectively, meaning their PGx information was available but not actively utilized in their care. This setup provides a unique baseline to assess the effectiveness of the MMC and the empowerment of EmPaSafe patients with PGx data, as we can analyse whether access to their genetic information and medication adjustments reduces ADRs and improves drug efficacy.
- Comparable Follow-up and Monitoring Protocols: The U-PGx control arm and the EmPaSafe study share similar follow-up methods, including regular monitoring for ADRs and the use of similar questionnaires. This similarity minimizes variation in data collection processes, allowing us to more directly compare ADR prevalence and other outcomes between the two groups.
- Matching for Key Variables: The control group will be matched to EmPaSafe participants based on age, sex, and type and number of medications, controlling for these variables in the analysis. This matching enhances the comparability of the two cohorts and strengthens the reliability of conclusions drawn about the impact of empowering patients with PGx data through the MMC.

Using the U-PGx control arm as a historical comparison thus allows EmPaSafe to evaluate the added value of PGx-informed care without needing a concurrent control group, streamlining the study while leveraging pre-existing data to explore the MMC's role in improving medication safety and personalization.

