#### • PGx profile

Additionally, the patients in The Netherlands, Greece and Slovenia will donate DNA by a blood sample by a venipuncture or through saliva, and will be genotyped within two weeks for our panel of 26 variants in 4 pharmacogenes (LUMC, UPAT and UL). The results of this PGx test Version number: 6, January 22nd, 2025 16 of 44

will be communicated through the MMC. Patients will be stimulated to share these results with their healthcare providers. This approach is used due to the patient centred nature of our study and MMC approach. Physicians will not receive any specific additional results other than what the patients share with them.

At the end of the 12-week study period, patients will have a semi-structured close out interview with the research nurses regarding the experience of the medication management centre.

• Gene and variant selection

The genes that will be tested are CYP2C19, CYP2C9, CYP2D6 and SLCO1B1 (see also Appendix 3). These all have actionable recommendations in the DPWG guidelines and are related to drugs frequently used in outpatients with polypharmacy. The selection of the genes is based on the drugs that were selected to be index drugs. Additionally, testing these genes is technically feasible and readily implemented in Leiden, Patras and Ljubljana. Updates in the guidelines of the DPWG will be taken into account during the project.

The variants chosen to study align with those studied by the Ubiquitous Pharmacogenomics (U-PGx) consortium. See Appendix 3 for the full pharmacogene and variant panel.

Genotyping

The method used to genotype the variants is up to the recruiting sites themselves. They must meet the following criteria: 1) test for the updated variant panel and 2) participate in proficiency testing programme to ensure quality of genotyping.

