# 4.4 Sample size calculation

As this is a proof-of-concept (PoC) pilot study, the sample size is aimed at showing the impact of the use of the MMC on patient empowerment and exploring associations, rather than statistically significant relations. Therefore, no formal sample size and power calculation is done. A number of 30 participants per site is the number of subjects that we estimate to be sufficient to investigate the impact of using the medication management centre and associated tools.

To explore potential effectiveness of the tool, results will be compared with those of matched historical controls obtained from the control arm of the U-PGx project. While the study is not aimed at or powered for statistical comparisons, we are in the unique position to have a access to a substantial cohort of comparable patients. Controls will be matched for age, sex and type and number of mediations. These results will help to design a larger study to perform a formal statistical analysis of the effect of the medication management system and associated tools.

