### Secondary clinical outcome:

- Total number of ADEs (related to index and subsequent drugs)
- Dose adjustments to index drug
- Drug cessation (and reason for discontinuation)
- Additional drugs that are prescribed during follow-up
- Routine drug levels (only those that are collected routinely) as a proxy for exposure
- Patient-reported drug adherence

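### The U-PGx comparison is meant to show the added value of PGx-informed care, but neither its matching variables nor its ADE outcome takes account of actionable genotype

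*Protocol*

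**What the plan says.** Protocol 3.1 gives three reasons why the U-PGx control arm is suitable. The first is that "Participants in the U-PGx control arm were genotyped retrospectively, meaning their PGx information was available but not actively utilized in their care". The section concludes that the design "allows EmPaSafe to evaluate the added value of PGx-informed care" without a concurrent control group.

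The matching variables appear twice, with the same content: in 3.1, "The control group will be matched to EmPaSafe participants based on age, sex, and type and number of medications", and in 4.4, "Controls will be matched for age, sex and type and number of mediations" (the last word is evidently a misprint for medications). Genotype and predicted phenotype are on neither list.

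The ADE outcome under 8.1.2 is "Total number of ADEs (related to index and subsequent drugs"), with no breakdown by genotype.

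The same comparison has a second purpose. Section 2.2 says "it will be investigated whether integrating the MMC into healthcare will lower the adverse drug event rate", and 8.1.2 repeats this. That concerns the whole MMC, which gives drug-drug interaction information to every participant (5.1, 5.1.1).

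Genotyping covers the Dutch, Greek and Slovenian participants only. The 30 German participants get the MMC without PGx testing (3.1, 8.2). Sections 4.4 and 10.2 make the secondary analyses descriptive and unpowered.

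**The concern.** Every index drug has an actionable guideline (Table 3), but taking such a drug is not the same as carrying a genotype that triggers it. Matching on type of medication balances drug exposure and leaves genotype to chance.

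Three things can move the ADE total between the cohorts: PGx-prompted changes in care (actionable patients only), the general MMC content (everyone), and whatever else differs between a current and a historical cohort. A single ADE total per cohort cannot separate them, although 3.1 promises a conclusion about the first.

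The genotypes needed for the separation exist for the controls and for three of the four sites, and they are part of the stated case for this control arm. Section 4.4 says the results will help design a larger study. A PGx estimate that is mostly dilution, or mostly MMC and cohort difference, would misinform that design.

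**Working it through.** The protocol states no effect size, ADE rate or power for this comparison, so there is no figure to reproduce. The working below shows the size of the dilution under stated assumptions.

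**Inputs from the protocol**
- 120 participants, 30 per country (3.1).
- Genotyped: 3 × 30 = 90, or 90/120 = 75% (8.2).

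**Assumptions (not in the documents)**
- Share *f* with a genotype actionable for a drug they take: 20% to 35%, that is 90 × 0.20 = 18 to 90 × 0.35 = 31.5, about 32 participants.
- True relative ADE reduction from PGx in those patients: 30%, and none in the others.
- ADE risk: (a) equal in both groups, or (b) 40% in actionable and 25% in other patients.
- For the sampling figures, one matched control per participant.

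**1. Dilution over the 90 genotyped participants**

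(a) Apparent reduction = *f* × 0.30:
- 0.20 × 0.30 = 6.0%
- 0.35 × 0.30 = 10.5%

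(b) Apparent reduction = (*f* × 0.40 × 0.30) / (0.25 + 0.15 × *f*):
- *f* = 0.20: 0.024 / 0.2800 = 8.6%
- *f* = 0.35: 0.042 / 0.3025 = 13.9%

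**2. Dilution over all 120**

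If the German participants have the same average ADE risk as the genotyped ones, multiply by 0.75:
- (a) 4.5% to 7.9%
- (b) 6.4% to 10.4%

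**3. Imbalance in actionable share when genotype is not matched**

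The 95% chance range for the difference in share between two groups of 90 is ±1.96 × √(2*f*(1−*f*)/90). This is ±11.7 points at *f* = 0.20, ±13.0 at the midpoint 0.275 and ±13.9 at 0.35.

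Under risks (b), a 13-point imbalance shifts the ADE comparison by 0.13 × 0.15 = 2.0 percentage points. Sampling error of the ADE difference itself, at an average risk of 0.29, is ±1.96 × √(2 × 0.29 × 0.71/90) = ±13.3 points. Imbalance is therefore the smaller problem.

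**4. Precision of the stratified description**

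The contrast of interest is the cohort difference in the actionable stratum minus that in the non-actionable stratum. Using risks (b), the same in both cohorts for the variance, and strata of 25 and 65 per cohort:

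±1.96 × √(2 × 0.40 × 0.60/25 + 2 × 0.25 × 0.75/65) = ±31 points.

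With 18 and 72 it is ±35 points, and with 32 and 58 it is ±29 points. The assumed effect is 0.40 × 0.30 = 12 points.

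**The case against.** The strongest reply is that the stated objective concerns the whole MMC (2.2, 8.1.2). For that question all participants are the right population, and a smaller average effect is not a bias. This stands, and the all-patient comparison should stay. It does not rescue the separate claim in 3.1 about PGx-informed care.

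A second reply is that the analysis plan may describe ADEs by genotype. It may. But the protocol itself fixes the matching list and the outcome, and it states the PGx purpose without tying either of them to genotype. Section 8.3 does mention using genetic information in descriptive analysis, but only for the main endpoints.

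A third reply is that the comparison is exploratory and the strata are small. That is correct, and it limits the remedy to description.

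A reader might also infer more than the documents support:
- **That both cohorts are fully genotyped.** The German quarter of EmPaSafe is not.
- **That omitting genotype from the matching causes the dilution.** Dilution comes from counting ADEs in everyone. The omission adds imbalance, which is small beside sampling error (steps 3 and 4). A 20% v 35% split in actionable share would lie just outside the chance range.
- **That the non-actionable stratum isolates historical bias.** It carries the general MMC effect as well.
- **That changing guideline versions will misclassify patients.** Section 3.2 does say "Updates in the guidelines of the DPWG will be taken into account during the project", but nothing says controls are classified under an older version, and 13.1 expects no major changes within 7 months. One common version is a precaution, not the repair of a shown error.

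**Conclusion.** The point holds for the PGx claim in 3.1 and not for the whole-MMC objective. Followed as written, the comparison cannot separate a PGx effect from the general MMC effect or from the difference between cohorts.

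Under the assumptions above, a 30% reduction in actionable patients would show as about 6-14% over the 90 genotyped participants, and about 4.5-10% if the German patients are included. These figures rest wholly on the assumed actionable share, ADE risks and effect. The mechanism does not depend on them. Because the comparison is secondary, descriptive and unpowered, this is an inexpensive improvement to the study's ability to address its own stated question, not a flaw that invalidates the study.

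**What to change.** In sections 3.1 and 8.1.2:

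1. Keep the all-patient matched comparison for the whole-MMC objective.
2. For the PGx claim, use only the Dutch, Greek and Slovenian participants and their matched controls.
3. Classify both cohorts, by the same four genes and one guideline version, as actionable or not for any drug taken during follow-up. Include subsequent drugs as well as the index drug, because the outcome counts ADEs from both. Fixing a version for analysis need not affect what is fed back to patients.
4. Describe ADEs separately in the two strata. Base any statement on PGx on the actionable stratum set beside the non-actionable one, and state that the latter reflects the general MMC effect plus historical bias.
5. Adding actionable status to the matching variables is optional. It cannot be applied to the German participants and does not by itself remove the dilution.

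If this is not done, the PGx claim in 3.1 should be withdrawn.

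The cost is protocol wording, re-translation of existing control genotypes and some extra description. The price in precision is about 18-32 actionable participants and intervals of roughly 30 points either way for the between-stratum contrast, so the result can only be exploratory.

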#### The EmPaSafe study design is depicted in figure 1.

Of note: UKA does not have the ability to genotype and will also not be able to report PGx results in a clinical setting and act upon it due to the German regulations. Due to the Arzneimit-telgesetz, which consists of strict regulations for clinical research that deal with drug effects (e.g., safety, efficacy, and pharmacokinetics), and the Gendiagnostikgesetz, which are regulations concerning pharmacogenetic diagnostics, it is not allowed to study actionable variants that are not in use in German clinical practice. However, the inclusion of data from the German site offers critical insights that enhance the robustness and applicability of the EmPaSafe study results. Although regulatory restrictions in Germany limit the use of PGx results to cases with specific medical indications, the observations gathered from the German cohort remain highly valuable for the study, contributing to broader objectives beyond PGx data alone. Below are three primary ways in which including the German population will provide valuable information to the EmPaSafe study:

- Comparability with the Target Population: The German cohort primarily consists of elderly, polymedicated patients—a group closely resembling the primary target population of the EmPaSafe study. These patients typically have complex medication regimens and could greatly benefit from improved medication safety and personalized care. By including data from this population, we enhance the comparability of findings across the study's international sites, including those in the Netherlands, Slovenia, and Greece, allowing us to evaluate the consistency of our results across diverse patient populations and contexts.
- Insights into Patient Empowerment and Health Literacy: The purpose of the MMC within EmPaSafe extends beyond the use of PGx information alone; it aims to increase patient

Version number: 6, January 22nd, 2025

empowerment and health literacy in medication management. Although PGx data usage is limited in Germany, the MMC still enables us to gather valuable information on how the tool impacts patients' understanding of, and engagement with, their medication. This is particularly useful to assess the broader functionality of the MMC as a patient-support resource, providing insights into its effectiveness in enhancing patient empowerment and health literacy independent of PGx information.

Enhanced Generalizability of Findings: By collecting data from Germany, a region with distinct legal, healthcare, and cultural contexts, we improve the generalizability of our study's results. This allows us to analyse whether the MMC's effectiveness in promoting patient empowerment and health literacy is consistent across different healthcare systems and regulatory frameworks. Such insights are essential for evaluating the potential applicability of the MMC in other European countries, especially those with similar regulatory constraints on PGx data usage.

In summary, the German site provides valuable data that extends beyond PGx-specific analysis. The inclusion of this site enables a comprehensive evaluation of the MMC's impact on patient empowerment, health literacy, and the general functionality of the tool across different European healthcare settings. This international perspective is essential for understanding the potential for broader implementation of EmPaSafe within Europe.

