# 3. STUDY DESIGN

## 3.1 Overall study design

This study is a multi-centre, open-label study to assess the impact of the developed MMC in combination with the developed risk score algorithms, patient-reported outcome tool, and model-based precision dosing tool on patient empowerment of polypharmacy patients, thereby improving drug safety. In the study, a total of 120 patients will be enrolled in The Netherlands, Greece, Slovenia, and Germany (30 patients per country). The study subjects will be followed for 12 weeks. At set time intervals (2 and 12 weeks) the subjects will be asked to complete a validated questionnaire through the eClinical Data Management Platform Castor (table 1), for which the patients receive an email and a reminder through the MMC. These questionnaires collect information on the experience with the MMC, clinical monitoring, clinical outcome, and adverse events.

Table 1. Overview of the questionnaires during the 12-week follow-up. The baseline questionnaire comprises of 97 questions, the 2-week questionnaire of 133 questions and the 12-week questionnaire of 206 questions. All questionnaires are adaptive.

	Baseline questionnaire	Adaptive questionnaire in the MMC at time point:	
		2 weeks	12 weeks
Experience			
Usability		Х	х
Health literacy	х		х
Clinical monitoring			
Comorbidities and allergies	х		
Concurrent medication and herbal	х	х	х
remedies (through patient diary)			
Clinical outcome			
Drug adherence	х	Х	х
Quality of Life	х		х
Adverse events			
Patient reported ADR		Х	х
Assessment of ADR severity		х	х
Pharmacogenomics			
DNA sample collection	Х		

The baseline questionnaire will additionally comprise questions covering in- and exclusion criteria, demographics, recruitment information, previous PGx test results, comorbidities and allergies, and the level of health literacy before use of the MMC. In total, the baseline questionnaire consists of 97 questions. The questionnaire offered two weeks after inclusion in the study consists of 133 questions. The last questionnaire, offered 12 weeks after inclusion in the study, consist of 206 questions. All questionnaires are adaptive meaning that the length and duration of the questionnaire depends on the answers of the participants.

[figure not shown]

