# 4. STUDY POPULATION

# 4.1 Population (base)

Polypharmacy patients of any ethnicity, which are over 18 years of age and within routine care receiving a first prescription for one of the index drugs (see table 3), are eligible to participate in the study. The participating centres will **focus on, but are not limited to**, recruiting within a specific therapeutic area that cover both in- and outpatient settings (see table 2). This diverse population is a reflection of the general polypharmacy population which allows us to assess the use of the MMC in this diverse and heterogenous group of patients.

Table 2. Centres participating to the study, with corresponding recruitment of patients. The centres are not limited to recruiting patients within these specific therapeutic areas and can also include patients outside them.

Site	Therapeutic focus for treatment	Number of patients in- cluded in total	Country/ Language
LUMC	Leiden University Medical Centre will in-	30	The Netherlands/
	volve community pharmacies in Leiden to		Dutch
	recruit patients.		
UPAT	Psychiatric patients will be recruited from	30	Greece/
	the psychiatric clinic of the General Uni-		Greek
	versity Hospital of Patras.		
UL	Primary care patients will be recruited	30	Slovenia/
	from three primary health care centres		Slovenian
	(Community Health Centre Ljubljana,		
	Family Medicine Clinic KUS and Health		
	Institute Zdravje)		
UKA	Polypharmacy patients from different	30	Germany/
	fields of medicine, above 60 years of age		German
	will be recruited in UKA's outpatient unit		
	for clinical pharmacology.		
Total for	study	120	

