#### 5.1.1 The medication management centre

All patients participating in the EmPaSafe study will gain access to the Medication Management Center (MMC), a digital platform developed to empower patients with information and enhance medication safety, particularly in cases of polymedication. The MMC's primary purpose is to serve as an educational resource that provides tailored, patient-specific insights into drug-drug interactions (DDIs) and drug-drug-gene interactions (DDGIs) based on individual pharmacogenomic (PGx) profiles. These insights aim to support adherence to therapy, improve patient outcomes, and mitigate risks associated with complex medication regimens.

The MMC annotates each patient's medication plan with curated safety information sourced from validated guidelines, including those from the Dutch Pharmacogenetics Working Group (DPWG), and trusted public databases such as the ABDA-Database. By offering personalized, high-quality content, the MMC helps patients understand their therapies and the potential risks associated with their medications. It also provides tools for reporting health concerns, such as adverse drug reactions (ADRs), through integrated patient-reported outcome measures (PROMs).

A core feature of the MMC is its emphasis on patient engagement. The platform equips users with the knowledge to have meaningful discussions with healthcare providers, thereby fostering collaborative decision-making. However, the MMC strictly serves an informational purpose; it neither facilitates self-adjustment of medication nor replaces professional medical advice. This distinction ensures compliance with regulatory requirements and underscores its role as an educational rather than a diagnostic tool.

The MMC also includes advanced functionalities that may shape the future of personalized medicine. These include exploratory tools, such as machine learning models and mechanistic risk assessments, designed to analyse real-world data for predicting adverse drug reactions (ADRs). While these tools are not yet clinically validated, they represent the innovative potential of integrating cutting-edge technologies into medication management.

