### 8.2 Randomisation, blinding and treatment allocation

No randomization will be applied. The Dutch, Slovenian and Greek patients will receive the MMC with PGx testing. The German patients will get access to the MMC, but will not receive any PGx testing. We will test the user experience.

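### Including Germany cannot show that the MMC effect is consistent across health systems, because German patients receive a different version of the intervention

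*Protocol*

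**What the plan says.** Protocol section 3.1 plans 120 patients, 30 in each of four countries, and explains why a site that cannot genotype is kept. Two of the reasons given matter here:

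- The German data are to show how the MMC performs without PGx, "providing insights into its effectiveness in enhancing patient empowerment and health literacy independent of PGx information".
- They are to widen generalisability, by showing whether the effect of the MMC on empowerment and health literacy "is consistent across different healthcare systems and regulatory frameworks". The same paragraph goes on to applicability in other countries, particularly those that also restrict the use of PGx data.

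Section 8.2 fixes who receives what: "No randomization will be applied. The Dutch, Slovenian and Greek patients will receive the MMC with PGx testing". It continues: "The German patients will get access to the MMC, but will not receive any PGx testing".

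Section 5.1.1 shows that PGx is no peripheral feature. It gives the main purpose of the MMC as tailored insight into "drug-drug interactions (DDIs) and drug-drug-gene interactions (DDGIs) based on individual pharmacogenomic (PGx) profiles". Section 4.3 excludes anyone already genotyped, so German participants should have no such profile from another source.

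Table 2 in section 4.1 describes the German recruits as "above 60 years of age", seen in an outpatient clinical pharmacology unit. The minimum age for the study is 18 (section 4.2). The primary endpoint in section 8.1.1 is defined once for all participants, with no distinction by PGx status.

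**The concern.** A statement about consistency across countries presupposes that the countries received the same intervention. Here the one country that represents a different regulatory framework also received a different version of the MMC, in patients with a different age focus and in a different clinical setting. These differences coincide at one site.

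At stake is what the study may conclude. If Germany shows a smaller change, the cause could be the missing PGx content, the older population, the clinic or the health system. If Germany shows a similar change, these influences may have offset one another. In neither case does the comparison support the statement in section 3.1. Because the endpoint is defined without regard to version, a reader of an all-site figure might also take it as the effect of one defined intervention.

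**Working it through.** **Inputs**

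- Four sites of 30 (section 3.1; Table 2): 4 × 30 = 120, which reproduces the stated total.
- PGx at three of the four sites, with no randomisation (section 8.2): 3 × 30 = 90 patients with MMC plus PGx, and 30 with MMC only.
- No significance level, SD, effect size or power is given (section 4.4), and the analysis is descriptive (section 10.1). My assumptions are a two-sided 5% level, 80% power where power is mentioned, a common SD of the change score, and complete data. Results are in SD units of the change.

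**Step 1. Can PGx and country be separated?** Write the change as an intercept, three country terms (Greece, Slovenia, Germany, against the Netherlands) and a PGx indicator. PGx equals 1 minus the German indicator, so the design matrix has 5 columns and rank 4. Only a combination can be estimated:

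Germany minus the others = (everything else that sets the German site apart) − (PGx effect)

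The same observed difference of −0.3 SD arises from each of these:

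| PGx effect | Other German effect | Observed difference |
|---|---|---|
| 0.3 | 0 | −0.3 |
| 0 | −0.3 | −0.3 |
| 0.15 | −0.15 | −0.3 |
| 0.6 | 0.3 | −0.3 |

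An observed difference of zero is no more informative: a PGx effect of 0.3 with another German effect of 0.3 gives 0.3 − 0.3 = 0.

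**Step 2. The three PGx sites alone.** An intercept and two country terms give 3 columns and rank 3, so differences between these sites can be estimated. Each still blends country with setting: community pharmacies in Leiden, a psychiatric clinic in Patras, primary care in Ljubljana.

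**Step 3. What a summary over all patients would mean.** The weights are 90/120 = 0.75 and 30/120 = 0.25. With an illustrative change of 0.5 SD at the PGx sites (an assumption) and a German change of 0.5, 0.2 or 0 SD:

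- 0.75 × 0.5 + 0.25 × 0.5 = 0.50
- 0.75 × 0.5 + 0.25 × 0.2 = 0.425
- 0.75 × 0.5 + 0.25 × 0 = 0.375

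The mix matters only if the two versions differ, which is the open question.

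**Step 4. Precision.** 95% half-widths of the mean change, 1.96/√n:

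- n = 120: 0.18 SD
- n = 90: 0.21 SD
- n = 30: 0.36 SD

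For the contrast of 30 with 90: 1.96 × √(1/30 + 1/90) = 1.96 × 0.211 = 0.41 SD. A true difference of 2.80 × 0.211 = 0.59 SD would be needed for 80% power. At 0.2, 0.3 and 0.5 SD the power is about 16%, 30% and 66%. Apparent similarity would thus be weak evidence even without the aliasing.

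**The case against.** The strongest reply is that section 3.1 gives a rationale and not an analysis. It names no contrast, test or estimator, and it does not say that Germany against the rest estimates a PGx or a country effect. The study is declared a proof of concept without formal power, the difference in intervention is openly disclosed, and tabulation by site could sit in a statistical analysis plan that is not shown. Consistency across regulatory frameworks might also be meant to include the PGx restriction itself.

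Much of this stands.

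- A reader might infer that the Protocol pools the four sites in its primary summary. It does not say so. Section 10.1 promises only descriptive statistics, and the overall score in section 8.1.1 reads most naturally as the questionnaire total.
- A reader might infer that an all-site figure or the German data would be meaningless. Neither follows. An all-site figure describes the MMC as delivered, with or without PGx. Germany's own before-after change describes MMC-only use, with the limits that any uncontrolled design has at every site.
- The age difference should not be overstated. Section 4.1 presents the site profiles as a focus and allows recruitment outside it.
- Setting differs at all four sites, so restricting the comparison to the PGx sites removes the difference in intervention but not the differences in setting and population.

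What the reply does not remove is the stated inference. A descriptive comparison also needs a common intervention before it can speak to consistency across health systems. The aliasing is fixed by the design, so no analysis model in a later plan can undo it.

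**Conclusion.** The consistency claim in section 3.1 is not supported where Germany is concerned. PGx status and the German site are completely aliased (rank 4 of 5), and age focus and setting differ as well. A German difference therefore cannot be attributed to health system, PGx or population, and similarity cannot be read as consistency. This rests on the design alone and needs no assumption about effect sizes.

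A summary over all 120 would be a 75:25 mix of two versions at planned enrolment, and should be read only as the MMC as delivered. The precision figures depend on the assumptions listed above, including no dropout.

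The defect lies in what the study says it can conclude. The data remain usable.

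**What to change.** 1. Define two versions of the intervention in sections 3.1 and 8.2: MMC with PGx, and MMC only.
2. Report the HLS-EU-Q47 primary outcome by version (planned n = 90 and n = 30) and by site. Label any all-site figure as a mix of the two.
3. Limit the cross-country consistency statement to the three PGx sites, noting that setting and population also differ among them, for example the psychiatric focus in Greece.
4. Present the German before-after change as a description of MMC-only use. State that the contrast of Germany with the other sites estimates neither a country effect nor a PGx effect.
5. Reconcile section 11.5, which says that a PGx profile will be obtained for every participant, with section 8.2.

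No new patients or data are needed. The cost is a few table rows and some wording, a wider interval for the group of 30 (half-width about 0.36 SD, against 0.18 SD for all 120), and a narrower claim of generalisability.
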